After the time of Discharge on the Day 90 Visit (Day 91), subject will enter a 28-day safety follow-up period during which there will be recording of spontaneously reported new AEs/SAEs and the active follow-up of ongoing AEs/SAEs by the study site. In

general, all AEs will be followed-up until resolved, stabilized (i.e., no worsening of the event), or a plausible explanation for the event has been found. The end of the study (EOS) is defined as the time of Discharge on Day 90 Visit (Day 91) plus 28-day follow-up.

Study Population and Main Criteria for Inclusion:

Female or male smoking, apparently healthy adult subjects without any restriction to races and ethnicities, meeting the following main inclusion criteria:

- Subject is aged with a minimum of 22 years(inclusive).
- Smoking, apparently healthy subject as judged by the Investigator.
- Subject smokes at least 10 commercially available mCC per day (no brand restrictions) for the last 4 weeks, based on self-reporting.
- Subject has smoked for at least the last 3 consecutive years.
- Subject does not plan to quit smoking within the next 6 months.
- Subject is ready to comply with the study protocol (e.g., to accept interruption of smoking for up to 91 days and to use THS 2.2 Menthol).

Investigational Products; Dose; and Mode of Use:

Test Product:

Tobacco Heating System 2.2 Menthol (THS 2.2 Menthol).

Reference Product:

The reference product to the THS 2.2 Menthol during the randomized exposure period is the subject's own preferred commercially available single brand of mCC.

Reference Point: SA.

Sample size:

Approximately one hundred and sixty smokers in the full analysis set (FAS) (~80 in THS 2.2 Menthol arm, ~40 in mCC and ~40 in SA) are required to attain 80% power to show at least a 50% reduction for any of the selected primary BoExp in THS 2.2 Menthol compared to the mCC arm, using a one-sided test with 2.5% type I error probability.

Data and information contained in this document are considered to constitute trade secrets and confidential commercial information, and the legal protections provided to such trade secrets and confidential information are hereby claimed under the provisions of United States law. No part of this document may be publicly disclosed without the written consent of Philip Morris International.

Statistical Methods:

Primary confirmatory endpoint: The hypothesis to be tested is that the geometric mean level of the BoExp for THS 2.2 Menthol is lower relative to mCC.

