12.1.5 Significance Level for Inferential Analysis

Unless stated otherwise, all statistical tests will be two-sided and conducted at the 5% level, and all quoted confidence intervals will be two-sided 95% confidence intervals.

The primary endpoints will be tested using a multiple testing procedure to preserve the overall alpha level by simultaneously testing the endpoints using a closed procedure with each test performed at an one-sided alpha level of 2.5%. This implies that statistical significance is required for all primary endpoints in order to be able to make confirmatory claims about any of the endpoints.

Further details will be provided in the SAP.

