Data and information contained in this document are considered to constitute trade secrets and confidential commercial information, and the legal protections provided to such trade secrets and confidential information are hereby claimed under the provisions of United States law. No part of this document may be publicly disclosed without the written consent of Philip Morris International.

Table 23 describes the expected power to demonstrate a reduction on 5 primary BoExp in smokers switching from CC to THS 2.2 Menthol as compared to those continuing to smoke mCC, using one-sided test with 2.5% type I error probability using the assumptions from YVD-CS01-EU and ZRHX-EX-01 given a sample size of 160 smokers (~80 in THS 2.2, ~40 in CC, and ~40 in the SA arm). Therefore subjects will be enrolled into the study until there are 160 smokers in the FAS population.

Table 23. Expected power (YVD-CS01-EU and ZRHX-EX-01 studies assumptions)

Assumptions	Reduction					
	50%	51%	52%	53%	54%	55%
YVD-CS01-EU	94%	88%	81%	70%	56%	38%
ZRHX-EX-01	98%	97%	92%	76%	41%	6%

Power considerations related to secondary endpoints of biological changes:

The sample size is sufficient to obtain 95% CIs for the ratio between (geometrical) mean levels of primary BoExp in THS 2.2 Menthol and SA with upper and lower limits deviating not more than 18% from the point estimates, with an 80% overall probability of achieving the desired precision of estimating the true mean.

This study has 80% power using a one-sided test with 2.5% type I error probability:

- To detect a 0.631 [mL/min/kg] (29%) difference between THS 2.2 Menthol and mCC in CYP1A2 activity, as measured by the caffeine clearance, assuming a SD of 0.564. Effect size and variability are derived from data obtained in the YVD-CS01-EU study sponsored by PMI.
- To detect a 24.71 [ng/g creatinine] (20%) difference between THS 2.2 Menthol and mCC in 11-DTX-B2, assuming a SD of 43.78, as reported by Saareks et al., 2001. The anticipated effect size of THS 2.2 Menthol is assumed to be about 90% of the effect of smoking cessation reported in the paper by Saareks et al., 2001.

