12.5 Primary Analysis

12.5.1 Primary Endpoint Analysis Variables

The primary endpoints are:

- COHb on Day 5
- MHBMA on Day 5
- 3-HPMA on Day 5
- S-PMA on Day 5
- Total NNAL on Day 90.

See Section 3.4.1.

Evaluation criterion:

The study will be considered successful, if the study demonstrates a 50% reduction or more for all five primary BoExp in the THS 2.2 Menthol arm compared to the mCC arm, using a one-sided test with 2.5% type I error probability.

Data and information contained in this document are considered to constitute trade secrets and confidential commercial information, and the legal protections provided to such trade secrets and confidential information are hereby claimed under the provisions of United States law. No part of this document may be publicly disclosed without the written consent of Philip Morris International.

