12.5.4 Confirmatory Analysis

The hypothesis to be tested is that the geometric mean level of the BoExp for THS 2.2 Menthol is lower relative to mCC.

For primary BoExp, the hypothesis will be tested on Day 5 for monohydroxylbutenyl-mercapturic acid (MHBMA), 3-hydroxypropylmercapturic acid (3-HPMA), S-phenylmercapturic acid (S-PMA), and carboxyhemoglobin (COHb), and on Day 90 Visit for Total NNAL.

The transformed BoExp data on a natural log scale will be analyzed by means of a generalized linear model using product arm as covariate adjusting for the following baseline information: sex, average cigarette consumption over the previous 4 weeks, and baseline value of endpoint. The test will be declared significant if the contrast THS 2.2 Menthol vs mCC is significant. Estimates of differences between groups will be back-transformed to provide relative effects.

Assumptions of the analysis of variance model will be tested. Markedly non-lognormally distributed BoExp data will be transformed or analyzed by appropriate non-parametric methods.

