**Table 20: Expected Power (YVD-CS01-EU and ZRHX-EX-01 Studies Assumptions)**

Assumptions	Reduction					
	50%	51%	52%	53%	54%	55%
YVD-CS01-EU	94%	88%	81%	70%	56%	38%
ZRHX-EX-01	98%	97%	92%	76%	41%	6%

A total of 160 smokers (80 in THS 2.2 menthol, 40 in mCC, and 40 in the SA arm) will be randomized to demonstrate a reduction of at least 50% on 5 primary BoExp in smokers switching from mCC to THS 2.2 Menthol as compared to those continuing to smoke mCC, using one-sided test with 2.5% type I error probability.

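### The synopsis ties 160 subjects to 80% power for the primary biomarkers, but Table 23 and the printed inputs give 94% or 98% for all five at that size

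*Protocol*

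**What the plan says.** The Sample size paragraph of the protocol synopsis states that about 160 smokers in the FAS (80 THS 2.2 Menthol, 40 mCC, 40 SA) "are required to attain 80% power to show at least a 50% reduction for any of the selected primary BoExp", "using a one-sided test with 2.5% type I error probability".

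Protocol 12.2 then says: "Table 23 describes the expected power to demonstrate a reduction on 5 primary BoExp in smokers switching from CC to THS 2.2 Menthol". At a 50% reduction with 160 smokers, Table 23 prints 94% under the YVD-CS01-EU assumptions and 98% under ZRHX-EX-01. SAP section 8 repeats the inputs and both figures (SAP Table 20) and makes no 80% claim.

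The success rule is joint. Protocol 12.5.1 calls the study successful if it "demonstrates a 50% reduction or more for all five primary BoExp in the THS 2.2 Menthol arm compared to the mCC arm", and 12.1.5 adds that "statistical significance is required for all primary endpoints in order to be able to make confirmatory claims about any of the endpoints".

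In 12.2 the figure 80% is attached only to secondary aims: precision of the comparison with SA, CYP1A2 activity, and 11-DTX-B2.

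On the count, 12.2 says: "Therefore subjects will be enrolled into the study until there are 160 smokers in the FAS population". The synopsis and Protocol 4.1 also count the FAS. Protocol 5.1 and SAP 6.1 count 160 randomized, and SAP section 8 says that 160 smokers "will be randomized to demonstrate a reduction of at least 50% on 5 primary BoExp".

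**The concern.** One protocol gives two different powers for the same size, margin and significance level. The synopsis also presents 160 as the number needed for 80%, which makes the primary endpoints look like the reason for 160 with nothing to spare. Its phrase covering any of the biomarkers does not describe a criterion that all five must meet. The synopsis is what many readers see first, so the stated power, the stated rule and the stated reason for the size should match the body.

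**Working it through.** **Inputs.** Mean ratios (MR) and CVs are from Protocol Table 19 (YVD-CS01-EU), Table 21 (ZRHX-EX-01) and Table 20 (Total NNAL, from the 12-week switching study). Table 22 gives 80:40 for the four Day 5 endpoints and 40:40 for Total NNAL, because 50% of the THS 2.2 Menthol arm is expected to leave the per-protocol (PP) set by Day 90. Protocol 12.5.4 fixes the scale: "The transformed BoExp data on a natural log scale will be analyzed by means of a generalized linear model".

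**Formulae.** Log SD = √ln(1 + CV²). Distance from the margin = ln(0.50/MR). SE = SD·√(1/n₁ + 1/n₂). Power is from the noncentral t at one-sided 2.5%. Joint power is the product over the five endpoints, assuming independence.

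**Reproducing the plan's 50% column.**

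| Endpoint | MR (CV) | Log SD | Distance | SE | Distance/SE | Power |
|---|---|---|---|---|---|---|
| COHb, YVD | 0.40 (0.32) | 0.312 | 0.223 | 0.0605 | 3.69 | 95.5% |
| 3-HPMA, YVD | 0.30 (0.50) | 0.472 | 0.511 | 0.0915 | 5.58 | 99.98% |
| MHBMA, YVD | 0.15 (0.70) | 0.632 | 1.204 | 0.122 | 9.85 | ≈100% |
| S-PMA, YVD | 0.20 (0.70) | 0.632 | 0.916 | 0.122 | 7.49 | ≈100% |
| COHb, ZRHX | 0.44 (0.14) | 0.139 | 0.128 | 0.0270 | 4.74 | 99.7% |
| Total NNAL, 40:40 | 0.30 (0.60) | 0.555 | 0.511 | 0.124 | 4.12 | 98.3% |

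The other three ZRHX-EX-01 endpoints are at about 100%.

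- YVD-CS01-EU: 0.9555 × 0.9998 × 1 × 1 × 0.9825 = 0.939, against 94% printed.
- ZRHX-EX-01: 0.9969 × 1 × 1 × 1 × 0.9825 = 0.979, against 98% printed.

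**Trying to recover 80%.**

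- Any read as each: at least 95.5%.
- Any read as at least one: about 100%.
- Any read as all five: 94% or 98%.
- Raw CV used as the log SD: 91.2% and 96.1%.
- Any correlation between endpoints (normal approximation): joint power stays within 94.3–95.8% (YVD-CS01-EU) or 98.2–98.5% (ZRHX-EX-01).
- Lower Day 90 retention: the THS 2.2 Menthol PP fraction would have to fall from 50% to about 18% (YVD-CS01-EU) or 16% (ZRHX-EX-01).

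The only entry near 80% in Table 23 is 81%, for a 52% reduction under YVD-CS01-EU, which is not the margin named in the synopsis.

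**The secondary 80% targets in 12.2.**

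- 11-DTX-B2 (difference 24.71, SD 43.78): SE at 80:40 = 43.78 × √(1/80 + 1/40) = 8.48, ratio 2.91, power about 82%. Reaching 80% takes about 152 in total at 2:1:1 (148 by the normal approximation).
- Precision against SA (Table 19 CVs, upper limit within 18%): S-PMA is the binding marker. The probability over the four Day 5 markers is about 87% at 80:40 and about 10% at 58:29.
- CYP1A2 (difference 0.631, SD 0.564): above 99.9% at 80:40, so this aim does not drive the size.

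**The case against.** The strongest reply is that the mismatch is harmless. 160 subjects do attain 80%, the correct figures are printed in Protocol 12.2 and SAP section 8, and no test, level or enrolment rule depends on the synopsis sentence. The synopsis evaluation criterion also names all five biomarkers, so nobody would apply an at-least-one rule. All of that stands, and it limits the point to a reporting correction. It does not rescue the claim that 160 are required for 80%.

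Three stronger readings are tempting, and the documents do not support them.

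- *The trial's power is wrong or inadequate.* Only the synopsis figure is wrong, and it understates the power.
- *The trial is oversized and could be cut.* On the primary inputs alone, 80% joint power needs about 112–116 subjects (YVD-CS01-EU) or 88–92 (ZRHX-EX-01). But 12.2 also sets the secondary targets above. At 116 subjects the SA precision target would be met with probability of only about 10%, and 11-DTX-B2 needs about 152.
- *Writing 160 randomized throughout is a wording change.* Protocol 12.2 enrols until the FAS reaches 160. The FAS (12.4.1) is a subset of those randomized, and 5.1.3 bars replacement after randomization. Moving to a randomized count could therefore leave fewer than 160 in the FAS.

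Table 23 is also not a clean reference throughout. ZRHX-EX-01 at 52% prints 92% against about 86% recomputed, and at 53% prints 76% against about 64%. YVD-CS01-EU at 55% prints 38% against about 44%. Rounded inputs may explain part of this. The 50% column, which is all this point uses, is unaffected.

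**Conclusion.** The point holds as a wording and reporting inconsistency in the synopsis. At 80:40:40 the plan's own inputs give 94% or 98% power for all five primary biomarkers, against the 80% stated: an understatement of 14 or 18 percentage points. The error is conservative and gives no ground for changing the sample size.

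The figures assume lognormal data with the printed ratios and CVs, no Day 5 exclusions, and 50% exclusion of the THS 2.2 Menthol arm from the Day 90 PP set. The 82% for 11-DTX-B2 counts all 80 THS 2.2 Menthol subjects; at the 40:40 Day 90 split it would be about 71%, which is a further reason not to reduce enrolment. The 80% in the synopsis may have been carried over from the secondary aims, but the documents do not say so.

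The FAS and randomized counts are a separate inconsistency, and that one can affect how many subjects are enrolled.

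**What to change.** Replace the synopsis sentence with: *About 160 subjects in the FAS (80:40:40) give 94% (YVD-CS01-EU inputs) or 98% (ZRHX-EX-01 inputs) power to show a reduction of at least 50% in all five primary BoExp in the PP set, one-sided 2.5%, assuming 50% of the THS 2.2 Menthol arm is excluded from the Day 90 PP set (Total NNAL 40:40, inputs from the 12-week switching study).* Add that the 80% figure belongs to the secondary aims in 12.2. Of these, SA precision and 11-DTX-B2 come close to needing 160. This is text only, with no change to enrolment or analysis.

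Separately, reconcile the FAS-based count (synopsis, Protocol 4.1 and 12.2) with the randomized count (Protocol 5.1, SAP 6.1 and SAP section 8). Choose one rule deliberately: if any randomized subject misses the FAS, the two rules stop enrolment at different points, so this choice is more than editorial.

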Table 18.	Time Schedule – Day 90 Visit (from the time of check-in in the morning prior to 08:30 AM of Day 90 to time of discharge of Day 91)	133
Table 19.	Expected Mean Ratios and Coefficients of Variation for THS 2.2 Menthol/mCC	148
Table 20.	Expected Mean Ratios and Coefficients of Variation for THS 2.2 Menthol/mCC	148
Table 21.	Expected Mean Ratios and coefficients of Variation for THS 2.2 Menthol/mCC	149
Table 22.	Sample Size to Assess the Reductions.....	149
Table 23.	Expected power (YVD-CS01-EU and ZRHX-EX-01 studies assumptions)	150
Figure 1.	Study Design.....	45
Figure 2.	Product Use Pattern Categorization.....	152

LIST OF APPENDICES

Appendix 1	Schedule of Events.....	172
Appendix 2	Participating Laboratories	184
Appendix 3	Investigational Product and Instructions for Use	185
Appendix 4	HST SODIM® Device Description	186
Appendix 5	Prochaska ‘Stage of Change’ Questionnaire.....	187
Appendix 6	Abnormal Laboratory Values	190
Appendix 7	Procedure for Nasal Epithelial Collection	194
Appendix 8	Procedure for Buccal Collection.....	196

LIST OF ABBREVIATIONS AND DEFINITIONS OF TERMS

Abbreviations

11-DTX-B2	11-dehydro-thromboxane B2
1-NA	1-aminonaphthalene
1-OHP	1-hydroxypyrene
2-NA	2-aminonaphthalene
3-HPMA	3-hydroxypropylmercapturic acid
4-ABP	4-aminobiphenyl
8-epi-PGF2 α	8-epi-prostaglandine F2 α
ADL	Activities of daily living
AE	Adverse event
ALT	Alanine aminotransferase
Apo A1	Apolipoprotein A1
Apo B	Apolipoprotein B
AP	Alkaline phosphatase
AST	Aspartate aminotransferase
B	Blood sample required
BMI	Body mass index
BoExp	Biomarker(s) of exposure
BP	Blood Pressure
BUN	Blood urea nitrogen
CAF	Caffeine
CC	Conventional cigarette
CD	Compact Disc
CDC	Centers for Disease Control and Prevention
CEMA	2-cyanoethylmercapturic acid
CFR	Code of Federal Regulations
CI	Confidence interval
CO	Carbon monoxide
COHb	Carboxyhemoglobin
CRO	Contract Research Organization
CSR	Clinical Study Report
CTCAE	Common Terminology Criteria for Adverse Events and Common

Data and information contained in this document are considered to constitute trade secrets and confidential commercial information, and the legal protections provided to such trade secrets and confidential information are hereby claimed under the provisions of United States law. No part of this document may be publicly disclosed without the written consent of Philip Morris International.

Toxicity Criteria

CTMS	Clinical Trial Management System
CV (statistics)	Coefficient of variation
CYP1A2	Cytochrome P450 1A2
CYP2A6	Cytochrome P450 2A6
DMP	Data Management Plan
DLCO	Diffusion capacity of lung for carbon monoxide
ECG	Electrocardiogram
eCRF	Electronic Case Report Form
ePRO	Electronic patient reported outcome
EOS	End of study
FAS	Full analysis set
FDA	Food and Drug Administration
FEV ₁	Forced expiratory volume in 1 second
FTND	Fagerström Test for Nicotine Dependence
FVC	Forced vital capacity
FRV	Forced residual volume
GCP	Good Clinical Practice
GGT	Gamma-glutamyl transferase
GVP	Gas vapor phase
HbA1c	Hemoglobin A1c
HDL	High density lipoprotein
HEMA	2-hydroxyethyl mercapturic acid
HIV	Human immunodeficiency virus
HMPMA	3-hydroxy-1-methylpropyl mercapturic acid
PHCs	Harmful and potentially harmful constituents
hs-CRP	High sensitive C-reactive protein
HST	Human smoking topography
IB	Investigator's Brochure
ICF	Informed consent form
ICH	International Conference on Harmonization
IC	Inspiratory capacity
IOM	Institute of Medicine
IP	Investigational Product
IRB	Institutional Review Board

Data and information contained in this document are considered to constitute trade secrets and confidential commercial information, and the legal protections provided to such trade secrets and confidential information are hereby claimed under the provisions of United States law. No part of this document may be publicly disclosed without the written consent of Philip Morris International.

ISO	International Organization for Standardization
IU	International unit
IV	Intravenous
IWRS	Interactive web and voice response system
LDH	Lactate dehydrogenase
LDL	Low density lipoprotein
LLN	Lower limit of the normal range
LLOQ	Lower limit of quantification
mCC	Menthol conventional cigarette
MCEQ	Modified Cigarette Evaluation Questionnaire
MCH	Mean corpuscular hemoglobin
MCHC	Mean corpuscular hemoglobin concentration
MCV	Mean corpuscular volume
MedDRA	Medical Dictionary for Regulatory Activities
MEF	Mid expiratory flow
MHBMA	Monohydroxybutenyl mercapturic acid
MNWS	Minnesota Nicotine Withdrawal Scale (revised version)
MR	Mean ratios
mRNA	messenger-ribonucleic acid
MRTP	Modified risk tobacco product
n	Number of subjects
NEQ	Nicotine equivalents
NNAL	4-(methylnitrosamino)-1-(3-pyridyl)-1-butanol
NNK	4-(methylnitrosamino)-1-(3-pyridyl)-1-butanone
NNN	N-nitrosornicotine
NRT	Nicotine replacement therapy
NSAID	Nonsteroidal anti-inflammatory drugs
o-tol	o-toluidine
PI	Principal Investigator
PK	Pharmacokinetic(s)
PMI	Philip Morris International
PP	Per-protocol
PT	Preferred term
PX	Paraxanthine
QC	Quality control

Data and information contained in this document are considered to constitute trade secrets and confidential commercial information, and the legal protections provided to such trade secrets and confidential information are hereby claimed under the provisions of United States law. No part of this document may be publicly disclosed without the written consent of Philip Morris International.

QSU	Questionnaire of Smoking Urges (brief version)
RBC	Red blood cell (count)
RNA	Ribonucleic acid
SA	Smoking abstinence
SAE	Serious adverse event
SAP	Statistical analysis plan
S-BMA	S-benzylmercapturic acid
SD	Standard deviation
SDTM	Standards Consortium's Study Data Tabulation Model
SES	Socio-Economic Status (questionnaire)
SHM	Sample Handling Manual
sICAM-1	Soluble inter-cellular adhesion molecule
SMAR	Smoking article
SMP	Safety management plan
SOC	System Organ Class
SOP	Standard operating procedure
S-PMA	S-phenylmercapturic acid
SQ	Smoking Questionnaire
T ₀	Start time of the first product use
TC	Total cholesterol
TG	Triglycerides
THS 2.2	Tobacco Heating System 2.2
TLC	Total lung capacity
TPM	Total particulate matter
U	Urine sample required
ULN	Upper limit of the normal range
ULOQ	Upper limit of quantification
USB	Universal Serial Bus
UV	Ultraviolet
VAS	Visual analog scale
VC	Vital capacity
WBC	White blood cell (count)
WHO	World Health Organization

Data and information contained in this document are considered to constitute trade secrets and confidential commercial information, and the legal protections provided to such trade secrets and confidential information are hereby claimed under the provisions of United States law. No part of this document may be publicly disclosed without the written consent of Philip Morris International.

Explanation of Terms

The following special terms are used in this protocol:

Baseline period	06:30 AM at Day -1 until 06:29 AM of Day 1.
Charger:	The function of the Charger (Model 4) is to recharge the Holder after use. It contains a battery with sufficient capacity to recharge the Holder approximately 20 times. It is a convenient size to carry around, and can itself be recharged from a mains power source.
Day 30 Visit, Day 60 Visit, and Day 90 Visit	Day 30 Visit, Day 60 Visit, and Day 90 Visit start on Day 30, Day 60, and Day 90 respectively at the time of check-in of the subject on site prior to 08:30 AM until the check-out of the day after respectively on Day 31, Day 61, and Day 91.
End of study	End of Study is defined as the time of discharge on Day 91 of the subject plus 28 days of safety follow-up.
Enrolment	On Day -2 for eligible subjects after all applicable inclusion and exclusion criteria have been satisfactorily met and the subject is willing and ready to use the THS 2.2 Menthol (the trial of THS 2.2 Menthol is the last assessment prior to enrolment).
Exposure period in confinement	06:30 AM of Day 1 until time of Discharge on Day 6.
Exposure period in the ambulatory setting	From the time of discharge on Day 6 until the time of Discharge on Day 90 Visit (Day 91).
mCC	The term 'menthol conventional cigarette' refers to manufactured and commercially available menthol cigarettes and excludes hand-rolled cigarettes, cigars, pipes, bidis, and other nicotine-containing products.
mCC incompatible with HST SODIM® device	All mCCs that are incompatible with the HST SODIM® device (e.g., slim mCC).

Data and information contained in this document are considered to constitute trade secrets and confidential commercial information, and the legal protections provided to such trade secrets and confidential information are hereby claimed under the provisions of United States law. No part of this document may be publicly disclosed without the written consent of Philip Morris International.

Randomization	Assignment of the subject randomization number in the Interactive Web and Voice Response System. This can be done any time on Day 0, however, subjects are not to be informed of their randomization group prior to Day 1.
Run-in period	Admission to site on Day -2 until 06:29 AM of Day -1.
Safety follow-up	After the time of Discharge on Day 90 Visit (Day 91), a 28-day safety follow-up will be done for the recording of spontaneously reported new adverse events (AEs)/serious adverse events (SAEs) and the active follow-up of ongoing AEs/SAEs by the site. In general, any AE will be followed-up until resolved, stabilized (i.e., no worsening of the event) or a plausible explanation for the event has been found.
Screening failure	Subjects who do not meet the entry criteria from the time of informed consent form signature to the time of enrolment will be considered a screening failure.
THS Menthol Tobacco Stick	The Menthol Tobacco Stick (product code C3 Menthol) contains tobacco which, when heated, generates an aerosol. It is custom-designed to be used with the Holder.
THS Tobacco Stick Holder (Holder)	The function of the Holder (Model 4.2) is to heat the Tobacco Stick, delivering an aerosol to the user. The electrical heating is powered from an internal battery which delivers power for about 6 minutes (allowing complete use of a single Menthol Tobacco Stick)
Time of Discharge	Time of Discharge on Day 6: time when the subject is released from the site (confinement period) after all the procedures of the day of Discharge (Day 6) have been conducted prior to entering into the ambulatory period Time of Discharge on Day 90 Visit (Day 91): time when the subject is released from the site and enters the 28-day safety follow-up period
Tobacco Heating Device	The Device comprises everything in THS 2.2 Menthol, except the Menthol Tobacco Stick

Data and information contained in this document are considered to constitute trade secrets and confidential commercial information, and the legal protections provided to such trade secrets and confidential information are hereby claimed under the provisions of United States law. No part of this document may be publicly disclosed without the written consent of Philip Morris International.

Tobacco Heating
System 2.2 Menthol
(THS 2.2 Menthol)

THS 2.2 Menthol comprises the following components: Menthol
Tobacco Stick, Holder, Charger, a Cleaning Tool, a mains power
supply, and a USB cable.

